11.4 Sample Size Estimate

The minimum sample size required to achieve 80% power using an alpha level of 0.05 (two-sided) and a 1:1 randomization ratio was computed based on a repeated measures study design that takes into account that the data are binary and can be correlated across repeated measurements (Rochon, 1998). We assumed a compound symmetry covariance structure to be conservative (correlation between 2 successive time points does not change over time), as well as a maximum correlation between any 2 time points of 0.65. The higher the assumed correlation between time points, referred to as phi, the less information that we gain from successive measurements, thus requiring a larger sample size. The assumption of 0.65 for the present study is based on the phi calculated for the stimulant UDS results from the subgroup of cocaine dependent participants in CTN-0009, a study that evaluated the impact of concurrently providing smoking-cessation treatment with substance-abuse treatment.

The probability of stimulant-free urines in the TAU group is another key assumption in determining sample size. A review of the stimulant UDS results for cocaine-dependent participants from three prior CTN studies, CTN-0009, CTN-0015 (Seeking Safety for women with PTSD and substance-use disorders), and CTN-0006 (Contingency management for stimulant abusers) produced probabilities ranging from 0.55 to 0.75, with the lower probabilities (i.e., 0.55) requiring larger sample sizes. Based on these prior studies, we assumed a probability of 0.6 for stimulant-free urines in the TAU group. A final key consideration in calculating sample size is the size of the group difference to be detected. The present study has been powered to detect the lower limit of a clinically meaningful effect. Specifically, this study will detect a group difference if the probability of stimulant-free urines in the TAU+SCT group is at least 0.7.

The sample size yielded from the assumptions outlined above is 528, with 264 in each treatment group. As described in section 11.6, an interim analysis to evaluate the accuracy of the assumptions made in calculating this sample size will be conducted, with an adjustment made to the sample size if needed.

11.5 Descriptive Statistics

Summaries of the characteristics of the participant population in both treatment arms at screening/baseline will be prepared for the intent-to-treat participants. A summary will be prepared to show dropouts/retention over time in each treatment group and for major subgroups. The number of missing observations will be compared between treatments and for major subgroups.

11.6 Interim Analyses

In coordination with the centralized Data and Statistics center (DSC), an interim check of the primary outcome measure for the control group (event rates, covariance and correlation matrices) will be conducted to assess the adequacy of the projected study sample size since this parameter is being estimated from limited

repeated measures data and involves several key assumptions that impact the required sample size. The analysis will be conducted when approximately 250 participants (about 125 in the control arm) have been enrolled and have completed the active treatment phase of the study. No interim analyses other than the check for the control group summary statistics to determine sample size adequacy are proposed for the trial. Specifically, an interim analysis to examine whether there is overwhelming evidence that one treatment is better or worse than the other (e.g., TAU+SCT is significantly better than TAU for stimulant use outcome) is determined to be unnecessary for the present protocol. This determination is primarily based on the fact that the outcome of interest, stimulant use, would only be indirectly impacted by the experimental treatment. Thus, while we expect to find a statistically and clinically significant treatment effect at the end of the study, we do not expect to find a large enough treatment effect to warrant an interim efficacy analysis. In addition, the results of five prior randomized placebo-controlled clinical trials of bupropion in stimulant abusers suggest that the potential for harm to the participants is minimal and, thus, an interim analysis to assess for potential harm is unnecessary.

A DSMB will monitor the progress of the present trial. An interim analysis could be performed to assess efficacy, futility, or safety if requested by the DSMB or NIDA. Trial monitoring guidelines for early stopping based on overwhelming benefit might be based on the Haybittle-Peto boundary, which requires p<.001 to stop a trial early (Pocock, 2005). The monitoring guidance for early stopping for lack of benefit or for futility might be based upon an approach of conditional probability (Jennison and Turnbull, 2000). Additional safety interim looks will be performed (without formal testing being performed) per the DSMB's request.

11.7 Minority/Gender Analyses

In accordance with NIH guidelines, repeated measures mixed model and GLMM analyses will be completed to determine whether treatment response was significantly affected by participant minority/gender status using an interaction term for treatment, time and minority/gender as appropriate.

11.8 Post-hoc Analyses

In addition to the analyses described above, a number of post-hoc analyses will be completed. Some examples of possible analyses include an exploration of participant screening/baseline variables that are predictive of treatment outcome, site characteristics associated with treatment outcome, and the impact that using different CO cut-off levels (e.g., 8 ppm vs. 4 ppm) has on the smoking outcome measures.

12.0 REPORTING AND MONITORING

Statement of Compliance

This trial will be conducted in compliance with the appropriate protocol, current Good Clinical Practice (GCP), the principles of the Declaration of Helsinki, and all other applicable regulatory requirements. Participating sites must obtain written approval of the study protocol, consent form, other supporting documents, and any advertising for participant recruitment from their local institutional review board (IRB) in order to participate in the study. Prior to study initiation, the protocol and the informed consent documents will be reviewed and approved by an appropriate Ethics Review Committee (ERC) or IRB. Any amendments to the protocol or consent materials must be approved before they are implemented. Annual progress reports and local Serious Adverse Event (SAE) reports will be submitted to each IRB, according to its usual procedures.

Regulatory Files

The regulatory files should contain all required regulatory documents, study-specific documents, and all important communications. Regulatory files will be checked at each participating site for the regulatory documents compliance prior to study initiation, throughout the study, as well as at the study closure.

12.1 Informed consent

The informed consent form is a means of providing information regarding the trial to a prospective participant and allows for an informed decision about participation in the study. Each study site must have the study informed consent approved by their IRB(s). A copy of the IRB-approved consent, along with the IRB study approval, must be sent to the Clinical Coordinating Center (CCC) and the lead node (LN) prior to the site initiation visit. Every study participant is required to sign a valid, IRB-approved current version of the study informed consent form prior to the initiation of any study related procedures. The site must maintain the original signed informed consent for every participant in a locked, secure location that is in compliance with their IRB and institutional policies and that is accessible to the study monitors. Every study participant should be given a copy of the signed consent form.

Prior to signing the informed consent form, research staff who are knowledgeable about the study will explain the study to the potential participant and provide the participant with a copy of the consent to read. If the participant is interested in participating in the study, a researcher who is authorized to obtain informed consent by the PI and if applicable by the IRB, will review each section of the informed consent form in detail, answer any of the participant's questions, and determine if the participant will consent by signing and dating the consent document. The person obtaining consent and a witness, if required by the local IRB(s), will also sign and date the consent document. The consent must be properly executed and complete to be valid. It is strongly recommended that another research staff member review the consent after it is signed to ensure that the consent is properly executed and complete. Persons delegated by the PI to obtain informed consent must be listed on the Staff Signature Log and must be approved by the IRB, if required. All persons obtaining consent must have completed appropriate training.

In order to ensure that potential study participants understand the research study, a comprehension "quiz" (referred to as a comprehension tool) may be administered to potential participants prior to the informed consent being signed. If the potential participant misses an item on the quiz, the research staff will re-review that information to ensure understanding of study procedures and may have the person re-take the consent quiz prior to signing the informed consent document. The content of the quiz may be modified per local IRB requirements.

The informed consent form must be updated or revised whenever important new safety information is available, or whenever the protocol is amended in a way that may affect a participants' participation in the trial. A copy of the informed consent will be given to a prospective participant to review during the consent process and to keep for reference. The participant will be informed that their participation is voluntary and they may withdraw from the study at any time, for any reason without penalty.

Individuals who refuse to participate or who withdraw from the study will be treated without prejudice. Study sites will be responsible for maintaining signed consent forms as source documents for quality assurance review and regulatory compliance.

Health Insurance Portability and Accountability Act (HIPAA)

Study sites may be required by their institutions to obtain authorization from participants for use of protected health information. Sites will be responsible for communicating with their IRBs or Privacy Boards and obtaining the appropriate approvals or waivers to be in regulatory compliance.

Investigator Assurances

Each community treatment program site (CTP) must file (or have previously filed) a Federal Wide Assurance (FWA) with the DHHS Office for Human Research Protection setting forth the commitment of the organization to establish appropriate policies and procedures for the protection of human research subjects, with documentation sent to NIDA or its designee. Research covered by these regulations cannot proceed in any manner prior to NIDA receipt of certification that the research has been reviewed and approved by the IRB provided for in the assurance (45 CFR 46.103(b) and (f)). Prior to initiating the study, the principal investigator at each study site will sign a protocol signature page, providing assurances that the study will be performed according to the standards stipulated therein.

12.2 Financial Disclosure

All investigators will comply with the requirements of 42 CFR Part 50, Subpart F to ensure that the design, conduct, and reporting of the research will not be biased by any conflicting financial interest. Everyone with decision-making responsibilities regarding the protocol must comply with their Institution's policy regarding conflict of interest.

12.3 Clinical monitoring

Investigators will host periodic visits by NIDA contract monitors who will ensure all study procedures are conducted and that study data are generated, documented and reported in compliance with the protocol, GCP, and applicable regulations. These monitors will audit, at mutually agreed upon times, regulatory documents, case report forms (CRFs), and corresponding source documents for each participant. Qualified node personnel (Node Protocol Managers and/or QA monitors) will provide site management for each site during the trial. This will take place as specified by the local protocol team, node PI or lead team and will occur as often as needed to help prevent, detect, and correct problems at the study sites. Node staff will verify that study procedures are properly followed and that site staffs are trained and able to conduct the protocol appropriately. If the node staff's review of study documentation indicates that additional training of

study personnel is needed, node staff will undertake or arrange for that training. Details of the contract, node

QA and data monitoring are found in the study QA monitoring plan.

12.4 Study documentation

Study documentation includes all case report forms, data correction forms, workbooks, source documents, monitoring logs and appointment schedules, sponsor-investigator correspondence, and signed protocol and amendments, Ethics Review Committee or Institutional Review Committee correspondence and approved consent form and signed participant consent forms.

Source documents include all recordings of observations or notations of clinical activities and all reports and records necessary for the evaluation and reconstruction of the clinical research study. Whenever possible, the original recording of an observation should be retained as the source document; however, a photocopy is acceptable provided that it is a clear, legible, and exact duplication of the original document.

12.5 Safety Monitoring

12.5.1 Data and Safety Monitoring Board (DSMB)

An independent CTN DSMB will examine accumulating data to assure protection of participants' safety while the study's scientific goals are being met. The CTN DSMB is responsible for conducting periodic reviews of accumulating safety and efficacy data. It will determine whether there is support for continuation of the trial, or evidence that study procedures should be changed, or if the trial should be halted, for reasons relating to the safety of the study participants, the efficacy of the treatment under study, or inadequate trial performance (e.g., poor recruitment).

12.5.2 Protocol Violations Reporting and Management

A protocol deviation is any departure from procedures and requirements outlined in the protocol. Protocol departures may occur on two levels, deviation versus violation. The difference between a protocol deviation and violation has to do with the seriousness of the event and the corrective action required. A protocol deviation is considered an action (or inaction) that by itself is not likely to affect the scientific soundness of the investigation or seriously affect the safety, rights, or welfare of a study participant. Protocol violations are departures that may compromise the participant safety, participant rights, inclusion/exclusion criteria or study data and could be cause for corrective actions if not rectified or prevented from re-occurrence. Protocol violations will be monitored at each site for (1) significance, (2) frequency, and (3) impact on the study objectives, to ensure that site performance does not compromise the integrity of the trial. The decision about whether a departure from the protocol will be designated as a protocol deviation or a protocol violation will be made by the protocol's Lead Investigator in conjunction with the CCC. The consequences will be specified and participating sites should be informed.

All protocol violations will be recorded in the Electronic Data Capture (EDC) system via the Protocol Violations CRF. Additionally, each site is responsible for tracking and reporting to their IRB as required. Protocol deviations will be noted by participating sites and reported to their IRBs as required. The CCC and the Data and Statistics Center and the Lead Investigator must be contacted immediately if an unqualified/ ineligible participant is randomized into the study.

12.5.3 Confidentiality

By signing the protocol signature page the investigator affirms that information furnished to the investigator by NIDA will be maintained in confidence and such information will be divulged to the IRB, Ethical Review Committee, or similar expert committee; affiliated institution; and employees only under an appropriate understanding of confidentiality with such board or committee, affiliated institution and employees. The lead investigator will obtain a federal Certificate of Confidentiality (CoC), protecting participants against disclosure of sensitive information (e.g., drug use), and will distribute it to all sites when received. The NIH office that issues the CoC will be advised of changes in the CoC application information. Participating CTP sites will be notified if CoC revision is necessary.

Participant records will be held confidential by the use of study codes for identifying participants on CRFs, secure storage of any documents that have participant identifiers, and secure computing procedures for entering and transferring electronic data.

12.5.4 Adverse Events (AEs)

The Lead Investigator (LI) may appoint a Study Clinician (MD, PhD, or PI) for this study, who will review or provide consultation for each Serious Adverse Event (SAE) as needed. These reviews will include an

assessment of the possible relatedness of the event to the study intervention or other study procedures. The Study Clinician will also provide advice for decisions to exclude, refer, or withdraw participants as required. In addition, NIDA will assign a Medical Monitor to this protocol to independently review the safety data, present it to the DSMB for periodic review, and provide PIs a Safety Letter when necessary. The medical monitor will determine which safety events require expedited reporting to NIDA, the DSMB and regulatory authorities. The study staff will be trained to monitor for and report adverse events and Serious Adverse Events.

Each of the CTPs has established practices for managing medical and psychiatric emergencies, and the study staff will continue to utilize these procedures. Treatment providers at each CTP will be responsible for monitoring participants for possible clinical deterioration or other problems, and for implementing appropriate courses of action.

12.5.4.1 Definitions of Adverse Event and Serious Adverse Event

Standard definitions for adverse events and serious adverse events, their identification, characterization regarding severity and relationship to therapy and processing are described in Appendix A.

12.5.4.2 Reportable Serious Adverse Events

For the present study, the following SAEs will not be recorded in the data system nor reported to IRBs.

- Admission to a hospital/surgery center for preplanned/elective surgeries;
- Admission to a hospital for scheduled labor and delivery

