11.3.3 Safety Analyses

1. Adverse events

Adverse events (AEs), including serious adverse events (SAEs), will be summarized by body system and preferred term using MedDRA (The Medical Dictionary for Regulatory Activities). Adverse events will be presented in two ways: (1) the number and proportion of participants experiencing at least one incidence of each event will be presented overall and by treatment group. The incidence of adverse events and serious adverse events by type will be compared between treatment arms using either Fisher's Exact mid-p-value or Chi-Square analysis as appropriate; and (2) a table displaying the total number of each event will be given overall and by treatment group. Listings of serious adverse events will be given, sorted by treatment, body system, and preferred term. Detail in these listings will include severity, relationship to study drug, and action taken as available.

2. Vital Signs

Repeated measures mixed models will be used to compare the treatment groups on blood pressure and heart rate from screening/baseline through study week 10.

3. The Hospital Anxiety and Depression Scale (HADS)

Repeated measures mixed models will be used to compare the treatment groups on depression and anxiety symptoms, as measured by the HADS, from screening/baseline through study week 10.

4. The Pittsburgh Sleep Quality Index (PSQI)

A repeated measures mixed model will be used to compare the treatment groups on the PSQI from screening/baseline through study week 10.

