17.0 APPENDIX A

17.1 Definition of Adverse Event and Serious Adverse Event

Adverse Event: An adverse event (AE) is defined as any reaction, side effect, or untoward event that occurs during the course of the clinical trial, whether or not the event is considered study-related or clinically significant. A new illness, symptom, sign or worsening of a pre-existing condition or abnormality is considered an AE. A thorough history during the eligibility assessment phase should record any chronic, acute, or intermittent preexisting or current illnesses, diseases, symptoms, or laboratory signs of the participant, to avoid reporting pre-existing conditions as new AEs and to assist in the assessment of worsening in intensity or severity of these conditions that would indicate an AE. Stable chronic conditions, such as arthritis, which are present prior to clinical trial entry and do not worsen are not considered AEs. The AE form is used to capture reportable AEs (as defined in the protocol) and also used to record follow-up information for unresolved events reported on previous visits. A study investigator will identify and characterize each AE, and follow appropriate reporting procedures.

Serious Adverse Event (SAE): A serious adverse event is defined as any untoward physical or psychological occurrence during the study that suggests a significant hazard, side effect, or precaution will be defined as an SAE. This includes, but may not be limited to any of the following events:

- Death: A death occurring during the study or which comes to the attention of the investigator during the protocol-defined follow-up after the completion of therapy, whether or not considered treatment-related, must be reported.
- Life threatening: Any adverse therapy experience that places the participant or participants, in the view of the investigator, at immediate risk of death from the reaction as it occurred (i.e., it does not include a reaction that had it occurred in a more serious form, might have caused death).
- In-patient hospitalization or prolongation of existing
- Persistent or significant disability or incapacity,
- Congenital anomaly/birth defect.
- An event that required intervention to prevent one of the above outcomes.

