17.3 Reporting and Management Procedures of AE/SAEs

Standard reporting, within 7 days of the site becoming aware of the event, is required for reportable AEs. Expedited reporting (within 24 hours of their occurrence and/or site's knowledge of the event) is required for reportable SAEs (including death and life-threatening events). A participating site must alert the NIDA-assigned Safety Monitor and the Lead Investigator of reportable SAEs within 24 hours of learning of the event. The SAE form and summary and any other relevant documentation should also be submitted with the initial report if adequate information is available at the time of the initial report to evaluate the event and provide a complete report. Local sites are responsible for reporting SAEs to their IRB, per their IRB's guidelines.

Additional information may need to be gathered to evaluate the SAE and to complete the AE and SAE forms. This process may include obtaining hospital discharge reports, physician records, autopsy records or any other type records or information necessary to provide a complete and clear picture of the SAE and events preceding and following the event. Within 14 days of learning of the event, an SAE form and related documents must be completed and entered into the data base. Documentation of the event that cannot be entered into the data base should be sent to the NIDA-assigned Safety Monitor. If the SAE is not resolved or stabilized at this time or if new information becomes available after the SAE form is submitted, follow-up SAE information must be submitted as soon as possible, but at least within 14 days after the site learns the information.

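### The SAE recording exemption for elective surgery is not limited to surgery planned before consent, so an elective in-patient admission for a new or worsened condition would be missing from the SAE comparison

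*Protocol*

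**What the plan says.** Section 12.5.4.2 of the protocol states that "the following SAEs will not be recorded in the data system nor reported to IRBs". Two kinds of event follow. The first is "Admission to a hospital/surgery center for preplanned/elective surgeries"; the second is a hospital admission for scheduled labor and delivery. Neither timing nor cause of the surgery is qualified.

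Appendix A, section 17.1, sets the definitions. On AEs it says "A new illness, symptom, sign or worsening of a pre-existing condition or abnormality is considered an AE", whether or not the event is study-related. Stable chronic conditions are set apart: those "which are present prior to clinical trial entry and do not worsen are not considered AEs". The SAE criteria include "In-patient hospitalization or prolongation of existing".

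Section 11.3.3 lists SAEs and states that "The incidence of adverse events and serious adverse events by type will be compared between treatment arms". On ethics reporting, section 17.3 says "Local sites are responsible for reporting SAEs to their IRB", following that IRB's guidelines, and section 12.0 likewise sends local SAE reports to each IRB under its usual procedures.

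**The concern.** The first bullet joins two different things with a slash. Surgery arranged before entry for an unchanged condition tells us nothing about the trial treatments. Elective surgery need only be non-emergency; it can be arranged during the trial for a problem that appeared or got worse after randomization. The bullet exempts both alike.

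At stake is whether the SAE tabulation matches the protocol's own definition of an SAE. The exemption acts when data are recorded, so an admission never entered as an SAE cannot be restored by anything written later in an analysis plan. Separately, a site whose IRB wants such admissions reported receives conflicting instructions.

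**Working it through.** There is no figure to reproduce and no arithmetic to run; this is a comparison of texts.

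1. **Take a test case.** After randomization a participant develops a new condition, or an existing one worsens, and is admitted as an in-patient for non-urgent scheduled surgery during the AE collection period (consent to 30 days after the last active treatment visit, section 17.1).

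2. **Apply section 17.1.** The new or worsened condition is an AE. The in-patient admission meets a seriousness criterion. The case is therefore an SAE, regardless of relatedness.

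3. **Apply section 12.5.4.2.** The admission is for elective surgery, so this SAE is not recorded as such and is not sent to IRBs. The protocol has the limiting idea available, since section 17.1 uses prior presence and absence of worsening to set aside stable chronic conditions, but section 12.5.4.2 does not use it.

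4. **Look for a later step that recovers the SAE.** The 24-hour alert to the Safety Monitor and Lead Investigator in section 17.3 covers reportable SAEs only. The monitors described in section 17.1 look for unreported reportable SAEs. The Safety Monitor's review in section 17.3 is of SAE reports, and here none is filed. The labor-and-delivery bullet differs: on-study pregnancies have their own CRF under section 17.1. Elective-surgery admissions have no equivalent form.

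5. **Establish what is still captured.** The bullet names the admission and not the condition that led to it. Section 17.1 says "The AE form is used to capture reportable AEs (as defined in the protocol"), and the only list in the protocol that restricts reportability is the SAE list of section 12.5.4.2. The condition therefore stays reportable as an AE, remains in the AE half of the section 11.3.3 comparison, is reviewed weekly by an investigator for seriousness, severity and relatedness (section 17.1), and reaches the DSMB in the AE summaries (section 17.3).

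6. **Net loss.** What drops out is the serious classification that rests on the elective admission, and with it one entry in the SAE listing, the SAE incidence comparison and the expedited route.

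7. **Compare the IRB clauses.** Section 12.5.4.2 says without exception that these SAEs are not reported to IRBs. Sections 12.0 and 17.3 make IRB reporting depend on the IRB's own rules, and the sentence in section 17.3 speaks of SAEs without the word reportable. Where an IRB requires such reports, a site cannot comply with all three sections.

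**The case against.** The strongest reply is that the bullet was meant narrowly. Next to scheduled labor and delivery, it can be read as covering admissions arranged in advance that represent no new untoward event, and on that reading nothing on-study is lost. That reading is possible, and the protocol nowhere says outright that admissions for new or worsened conditions are exempt. But it makes the word elective redundant and leaves each of about 12 sites to supply the limit for itself.

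A second reply is that the scope is small. Urgent and unplanned admissions remain reportable. A case that meets another seriousness criterion is not exempted on that ground. A same-day procedure at a surgery center would not by itself be in-patient hospitalization. All of this stands.

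A third reply is that section 12.5.4.2 is a specific exception to the general IRB rule. That softens the conflict but does not remove it, because sections 12.0 and 17.3 defer to the IRB and carry no such exception. This part is a drafting matter and has no bearing on the arm comparison.

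A reader might also infer three stronger things, none of which the documents support:

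- **That these events disappear from view of the investigators and the DSMB.** They do not; the underlying condition is recorded and reviewed as an AE.
- **That the SAE count is understated by some stated percentage.** The protocol gives neither a rate of elective admissions nor an expected SAE rate, so any percentage would be one assumption divided by another.
- **That the arm comparison is biased.** The rule is the same in both arms. Staff will generally know the arm when they judge whether an admission is elective, because TAU has no placebo, but nothing in the protocol shows that the judgment would differ by arm.

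**Conclusion.** The point holds as a mismatch between the exemption and the protocol's own SAE definition. On a literal reading of section 12.5.4.2, an elective in-patient admission for a condition that is new or worse on study qualifies as an SAE under section 17.1 and is left out of the SAE listing, the SAE comparison and expedited reporting. The loss is confined to the serious label; the AE record remains. The number of cases cannot be estimated from the documents and may be zero. The efficacy analyses are not affected. The IRB clause needs reconciling with sections 12.0 and 17.3 in any case. The matter is minor but inexpensive to put right.

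The conclusion rests on two readings: that elective is taken in its ordinary sense of non-emergency, and that the bullet exempts the admission and not the condition behind it.

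**What to change.** In section 12.5.4.2, reword the first bullet along these lines: *admission for surgery that was scheduled before consent, for a condition that has not worsened since consent*. State that all other surgical admissions follow the definitions of section 17.1 and the reporting rules of section 17.3. Replace the closing clause on IRBs with: *and are reported to IRBs only where the IRB requires it*. Sections 12.0, 12.5.4.2, 17.1 and 17.3 then agree.

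The cost is one reworded bullet, one reworded clause and a few additional SAE forms at most.
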